6.1.2 Pre-medication prior to Administration of RO7296682

No pre-medication is foreseen prior to the administration of RO7296682, unless per Investigator judgment and based on the participants' medical history, pre-medication is warranted in the best interest of the participant. In case of IRRs, a list of pre-medication is provided in [Table 8](#). Pre-medications are captured in a dedicated pre-medication eCRF.

For participants having experienced an IRR-like reaction with a single and isolated symptom such as fever, occurring within 24 h after study drug infusion was completed, the use of pre-medication such as paracetamol, antihistamines and corticosteroids is not foreseen prior to subsequent RO7296682 administrations. Pre-medication of those participants at subsequent infusions is at the discretion of the investigator, as is the

treatment and management at the time of an event. The event will be reported as a single AE (e.g. fever).

Table 8 Pre-medication prior to Treatment with RO7296682

First Infusion	Subsequent Infusions

Pre-medication with the following can be considered at Investigator discretion approximately 30 minutes prior to the infusion:
 
• Antihistamines (both an H1-receptor antagonist and an H2-receptor antagonist) and/or• Antipyretics per institutional standard and/or• Anti-emetic	
In case of IRR Grade 1 at previous infusion Pre-medication with the following is recommended approximately 30 minutes prior to the infusion:
 
• Antihistamines (both an H1-receptor antagonist and an H2-receptor antagonist) and/or• Antipyretics per institutional standard and/or• Anti-emetic 
In case of IRR Grade 2 at previous infusion pre-medication with the following must be administered approximately 30 minutes prior to the infusion:
 
• Antihistamines (both an H1-receptor antagonist and an H2-receptor antagonist) and• Anti-pyretics per institutional standard and/or• Anti-emetic 
In case of IRR Grade 3 at previous infusion, pre-medication with the following must be administered approximately 30 minutes prior to the infusion:
 
• Antihistamines (both an H1-receptor antagonist and an H2-receptor antagonist) and• Anti-pyretics per institutional standard and• Hydrocortisone (200 mg IV or equivalent according to institutional guidelines) and/or• Anti-emetic 
In case of IRR Grade 4, treatment with RO7296682 and must be permanently discontinued and patient discontinued.

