
 For pre-medication guidelines, refer to Table 8. Vital signs (pulse rate, respiratory rate, blood pressure, and temperature) should be measured within 60 min prior to the infusion. RO7296682 should be infused over 4 h (± 15 min). If clinically indicated, vital signs should be measured every 15 (± 5) min during the infusion and at 30 (± 10) min after the infusion. Participants should be informed about the possibility of delayed post-infusion symptoms and instructed to contact their study physician if they develop such symptoms. 	
 If the participant experienced Grade ≥ 2 IRR with any previous infusion, refer to the pre-medication guidelines in Table 8. Vital signs should be measured within 60 min prior to the infusion. RO7296682 should be infused over 2 h (± 10 min) if the first infusion was well tolerated (i.e., absence of Grade ≥ 2 IRRs). If the 2 h infusion was well-tolerated, all subsequent infusions may be reduced to 60 (± 10) min. If the participant experienced Grade ≥ 2 IRRs the previous infusion duration should be maintained until absence of Grade ≥ 2 IRRs is observed. If the participant experienced an IRR with the previous infusion or if clinically indicated, vital signs should be measured during the infusion and at 30 (± 10) min after the infusion.

Figure 3 Infusion Times of Atezolizumab followed by RO7296682

*In case of Grade ≥ 2 IRRs, refer to [Table 6](#) and [Table 7](#) for infusion durations.

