CRS is defined as a supraphysiologic response following administration of any immune therapy that results in activation or engagement of endogenous or infused T cells and/or other immune effector cells. Symptoms can be progressive, always include fever at the onset, and may include hypotension, capillary leak (hypoxia), and end-organ dysfunction (Lee et al. 2019). CRS has been well documented with chimeric antigen receptor T-cell therapies and bispecific T-cell engager antibody therapies but has also been reported with immunotherapies that target PD-1 or PD-L1 (Rotz et al. 2017; Adashek and Feldman 2019), including atezolizumab.

There may be significant overlap in signs and symptoms of IRRs and CRS, and in recognition of the challenges in clinically distinguishing between the two, consolidated guidelines for the medical management of IRRs and CRS are provided in Table 12.

Severe COVID-19 appears to be associated with a CRS involving the inflammatory cytokines interleukin (IL)-6, IL-10, IL-2, and IFN- γ (Merad and Martin 2020). If a participant develops suspected CRS during the study, a differential diagnosis should include COVID-19, which should be confirmed or refuted through assessment of exposure history, appropriate laboratory testing, and clinical or radiologic evaluations per Investigator's judgment. If a diagnosis of COVID-19 is confirmed, the disease should be managed as per local or institutional guidelines.

Table 12 Management Guidelines for Infusion-Related Reactions and Cytokine-Release Syndrome

Event	Management
Grade 1^a Fever ^b with or without constitutional symptoms	
 Immediately interrupt infusion. Upon symptom resolution, wait for 30 minutes and then restart infusion at half the rate being given at the time of event onset. If the infusion is tolerated at the reduced rate for 30 minutes, the infusion rate may be increased to the original rate. If symptoms recur, discontinue infusion of this dose. Administer symptomatic treatment,^c including maintenance of IV fluids for hydration. In case of rapid decline or prolonged CRS (>2 days) or in participants with significant symptoms and/or comorbidities, consider managing as per Grade 2. For subsequent infusions, consider administration of oral pre-medication with antihistamines, antipyretic medications, and/or analgesics, and monitor closely for IRRs and/or CRS.

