Grade 3^a Fever ^b with hypotension requiring a vasopressor (with or without vasopressin) and/or Hypoxia requiring high-flow oxygen ^d by nasal cannula, face mask, non-rebreather mask, or Venturi mask	
 Permanently discontinue RO7296682 and/or atezolizumab and contact the Medical Monitor.^f Administer symptomatic treatment.^c For hypotension, administer IV fluid bolus and vasopressor as needed. Monitor cardiopulmonary and other organ function closely; monitoring in the ICU is recommended. Administer IV fluids as clinically indicated, and manage constitutional symptoms and organ toxicities as per institutional practice. Rule out other inflammatory conditions that can mimic CRS (e.g., sepsis). If no improvement within 24 hours, initiate workup and assess for signs and symptoms of HLH or MAS as described in Appendix 12. Administer IV corticosteroids (e.g., methylprednisolone 2 mg/kg/day or dexamethasone 10 mg every 6 hours). Consider anti-cytokine therapy.^e Hospitalize participant until complete resolution of symptoms. If no improvement within 24 hours, manage as per Grade 4, that is, admit participant to ICU and initiate hemodynamic monitoring, mechanical ventilation, and/or IV fluids and vasopressors as needed. For participants who are refractory to anti-cytokine therapy, experimental treatments may be considered at the discretion of the Investigator and in consultation with the Medical Monitor.

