- ^b Fever is defined as temperature $\geq 38^{\circ}\text{C}$ not attributable to any other cause. In participants who develop CRS and then receive anti-pyretic, anti-cytokine, or corticosteroid therapy, fever is no longer required when subsequently determining event severity (grade). In this case, the grade is driven by the presence of hypotension and/or hypoxia.
- ^c Symptomatic treatment may include oral or IV antihistamines, *antipyretic medications*, analgesics, bronchodilators, and/or oxygen. For bronchospasm, urticaria, or dyspnea, additional treatment may be administered as per institutional practice.
- ^d Low flow is defined as oxygen delivered at ≤ 6 L/min, and high flow is defined as oxygen delivered at > 6 L/min.
- ^e There are case reports where anti-cytokine therapy has been used for treatment of CRS with immune CPIs (Rotz et al. 2017; Adashek and Feldman 2019), but data are limited, and the role of such treatment in the setting of antibody-associated CRS has not been established.
- ^f Resumption of RO7296682 and/or atezolizumab may be considered in participants who are deriving benefit and have fully recovered from the event. Participants can be re-challenged with RO7296682 and/or atezolizumab only after approval has been documented by the Investigator (or an appropriate delegate) and the Medical Monitor. For subsequent infusions, administer oral pre-medication with antihistamines, *antipyretic medications*, and/or analgesics, and monitor closely for IRRs and/or CRS. Pre-medication with corticosteroids and extending the infusion time may also be considered after consulting the Medical Monitor and considering the benefit–risk ratio.
- ^g Refer to Riegler et al. (2019) for information on experimental treatments for CRS.

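### Tables 8 and 12 give different default actions after a Grade 3 infusion-related reaction and neither says which governs; Table 12 also has no row for an afebrile, non-hypoxic hypotensive reaction

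*Combined protocol and SAP*

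**What the plan says.** **Infusion and pre-medication rules (Sections 6.1.1 and 6.1.2).** For later RO7296682 infusions, Table 7 states: "If the participant experienced Grade ≥ 2 IRR with any previous infusion, refer to the pre-medication guidelines in Table 8". It also keeps the previous infusion duration until no Grade ≥ 2 IRR is seen. It makes no exception for Grade 3. Table 8 then sets pre-medication by grade. For Grade 3: "In case of IRR Grade 3 at previous infusion, pre-medication with the following must be administered approximately 30 minutes prior to the infusion". The list is antihistamines, antipyretics and hydrocortisone, with an anti-emetic under an and/or. For Grade 4: "In case of IRR Grade 4, treatment with RO7296682 and must be permanently discontinued and patient discontinued". Table 8 names no grading scale and does not refer to Table 12.

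**Management rules (Section 8.3.9.2).** The text says that "consolidated guidelines for the medical management of IRRs and CRS are provided in Table 12". The Grade 3 row opens "Permanently discontinue RO7296682 and/or atezolizumab and contact" the Medical Monitor. Footnote f, attached to the Grade 3 and Grade 4 rows, limits resumption to participants who are deriving benefit and have fully recovered, and adds: "Participants can be re-challenged with RO7296682 and/or atezolizumab only after approval has been documented by the Investigator (or an appropriate delegate) and the Medical Monitor".

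**Grading in Table 12.** Footnote a bases the management grades on the ASTCT consensus scale for cytokine-release syndrome (CRS) and uses NCI CTCAE v5.0 for reporting severity. All four grade definitions start from fever. Footnote b drops the fever requirement only for participants who have developed CRS and were then given antipyretic, anti-cytokine or corticosteroid therapy.

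**The concern.** Two parts of one protocol answer the same bedside question differently: may RO7296682 be given again after a Grade 3 IRR? Table 8 reads as yes, with pre-medication. Table 12 reads as no, unless re-challenge is approved and documented. The infusion tables are what site staff use when preparing the next dose, so the more permissive instruction may be the one in hand.

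The stake is participant safety. Section 8.3.9 lists IRRs among the most common toxicities expected from RO7296682 and describes this as the first human evaluation of the combination. Different sites could handle the same event differently.

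The fever requirement is a smaller matter of the same kind. Section 8.3.9.2 says that CRS always includes fever at onset, but names fever as only one possible IRR symptom, alongside hypotension. A scale built for CRS can therefore leave some IRRs unplaced.

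**Working it through.** No arithmetic applies. The check sets the rules side by side.

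**1. Action after the event**

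| | Table 8 (with Table 7) | Table 12 (with footnote f) |
|---|---|---|
| Grade 3, default | Required pre-medication, then next RO7296682 infusion | Permanent discontinuation |
| Grade 3, condition for re-dosing | None stated | Benefit, full recovery, documented approval by Investigator and Medical Monitor |
| Grade 4, default | Permanent discontinuation | Permanent discontinuation |
| Grade 4, exception | None | Footnote f re-challenge |

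The defaults differ at Grade 3. At Grade 4 they agree, and only the exception differs.

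**2. Is Table 8 only a pre-medication list?** Its title and introduction suggest so. But its Grade 4 line is a stopping rule. A table that stops at Grade 4, and for Grade 3 prescribes what precedes the next infusion, tells its reader that Grade 3 continues. Table 7 supports that reading by sending every prior Grade ≥ 2 IRR there.

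**3. Do other provisions supply the missing approval?**
- Section 6.6 requires resolution to Grade 1 or baseline before resuming. A resolved Grade 3 IRR meets this; Medical Monitor approval is needed only for exceptions.
- Section 7.1.1 asks for discussion with the Medical Monitor before restart after an interruption. Discussion is not documented approval.
- Section 8.3.9 allows departure from the guidelines after consulting the Medical Monitor. It does not say which of two guidelines is the default.
- Section 8.3.6 has IRR events reported within 24 hours. That informs the Sponsor but does not control dosing.
- In Part I, Section 4.1.2.1 counts non-hematological toxicity of Grade ≥ 3 in the DLT window as a DLT, subject to exceptions that are redacted. Section 6.6 says participants with a DLT should stop, or may have a reduced RO7296682 dose after discussion with the Sponsor. The window runs to 7 days after the second administration. If IRRs are not among the exceptions, this covers reactions to the first two Part I infusions. It does not cover later infusions, or Parts II and III.

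**4. Placing an afebrile reaction.** Take an IRR with hypotension, no fever at any time and no hypoxia. Grade 1 is fever with or without constitutional symptoms. Grades 2 to 4 are fever with hypotension, and/or hypoxia, at rising levels of support. The case fits none of them, even if a vasopressor is needed. Footnote b does not help, because it presupposes CRS that has developed and been treated. It also does not address fever suppressed beforehand by the antipyretic and corticosteroid listed in Table 8. The case falls to Investigator judgment under Section 8.3.9.

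**The case against.** The best defence is that Table 8 comes after Table 12: a participant approved for re-challenge under footnote f still needs pre-medication, and Table 8 supplies it. Section 6.1 sends discontinuation to Sections 6.6 and 7, and Section 8.3.9 sends IRR management to Table 12. That would be a sensible arrangement, and the fix below adopts it. But neither table states it, and Table 8's Grade 4 stop, without footnote f's exception, suggests that it was not written that way. Footnote f also gives its own pre-medication advice ("Pre-medication with corticosteroids and extending the infusion time may also be considered after consulting the Medical Monitor") without pointing to Table 8. Little should rest on the contrast with hydrocortisone in Table 8: the and/or there leaves its mandatory status open to argument, and giving a corticosteroid is compatible with footnote f.

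A second defence is that the grades may lie on different scales, so that a Grade 3 event in one table need not be one in the other. This stands as a caution. It makes it harder for a site to know which rule applies; it does not reconcile them.

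On the missing row, some afebrile reactions are covered elsewhere. Section 6.1.2 leaves a single isolated symptom within 24 hours after infusion to the Investigator, Section 7.1 lists IgE-mediated hypersensitivity as a reason to discontinue, and footnote c to Table 12 covers treatment of bronchospasm, urticaria and dyspnea. What remains is narrower, for example non-allergic hypotension during an infusion.

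**Conclusion.** The conflict over the default action after a Grade 3 IRR is real on the text and should be corrected. The missing Table 12 row is a genuine but secondary gap. The documents give no IRR rate, so no number of participants or infusions can be attached to either. Neither bears on sample size, power or error rates.

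The conclusion assumes that at least some events are Grade 3 under both tables. How much Part I is protected depends on the redacted DLT exceptions.

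Three stronger readings are not supported:
- A reader might infer that the tables also conflict at Grade 4. Both discontinue by default there; only Table 12 adds a permissive exception.
- A reader might infer that the protocol re-doses participants with a history it excludes at entry. Exclusion criterion 4 concerns reactions to previous checkpoint inhibitor treatment, and RO7296682 is an anti-CD25 antibody.
- A reader might infer that re-dosing would proceed without oversight. Sections 6.6, 7.1.1 and 8.3.6 provide some; what they lack is footnote f's documented approval.

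**What to change.** 1. In Table 8, state that re-dosing with RO7296682 after a Grade 3 IRR happens only under Table 12 footnote f, with Table 8 then giving the pre-medication.
2. State whether footnote f applies to RO7296682 after a Grade 4 IRR.
3. In Table 12, state that for IRRs the hypotension and hypoxia criteria apply whether or not fever is present, including when antipyretic or corticosteroid pre-medication was given.

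Item 3 keeps the existing scale. Reassigning Table 12 rows by CTCAE grade is not advised: it could change which reactions trigger permanent discontinuation, and the documents do not contain the definitions needed to check the effect.

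The cost is a few lines in a protocol amendment, with no new procedures or data. The small downside is an added approval step before some re-dosing.

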6.2 PREPARATION/HANDLING/STORAGE/ACCOUNTABILITY

Study drug packaging will be overseen by the Sponsor's clinical study supplies department and bear a label with the identification required by local law, the protocol number, drug identification and dosage.

The packaging and labeling of the study medication will be in accordance with the Sponsor's standard and local regulations. RO7296682, RO7296682 diluent and atezolizumab will be provided by the Sponsor.

The investigational site will acknowledge receipt of IMPs and confirm the shipment condition and content. Any damaged shipments will be replaced. The Investigator or designee must confirm that appropriate temperature conditions have been maintained during transit for all IMPs received and that any discrepancies have been reported and resolved before use of the IMPs. All IMPs must be stored in a secure, environmentally controlled, and monitored (manual or automated) area in accordance with the labeled storage conditions, with access limited to the investigator and authorized staff.

The study site (i.e., Investigator or authorized personnel [e.g., pharmacist]) is responsible for study treatment accountability, reconciliation, and record maintenance (i.e., receipt, reconciliation and final disposition records). Upon arrival of the IMPs at the site, site personnel will complete the following:

- Check the IMPs for damage.
- Verify proper identity, quantity, integrity of seals and temperature conditions.
- Report any deviations or product complaints to the Study Monitor upon discovery.

The qualified individual responsible for dispensing the study treatment will prepare the correct dose according to the Pharmacy Manual.

Only participants enrolled in the study may receive study treatment and only authorized site staff may supply or administer study treatment.

IMPs will either be disposed of at the study site according to the study site's institutional standard operating procedure or returned to the Sponsor with the appropriate documentation. The site's method of IMP destruction must be agreed upon by the Sponsor. Local or institutional regulations may require immediate destruction of used IMP for safety reasons. The site must obtain written authorization from the Sponsor before any IMP is destroyed, and IMP destruction must be documented on the appropriate form. Accurate records of all IMPs received at, dispensed from, returned to, and disposed of by the study site should be recorded on the drug accountability log.

Refer to the Pharmacy Manual and the [RO7296682](#) and [atezolizumab](#) Investigator's Brochure for information on IMP formulation, IMP handling, including preparation and storage, and accountability.

6.3 MEASURES TO MINIMIZE BIAS: RANDOMIZATION AND BLINDING

6.3.1 Method of Treatment Assignment

This is an open-label study with no randomization.

The Sponsor will be responsible for allocation of patient numbers, using an IxRS process. The log in information and directions for the IxRS will be provided to each site.

Participants who fulfill all of the inclusion criteria and none of the exclusion criteria are eligible to participate in the study and will be assigned to a treatment group/dose in consultation with the Sponsor.

6.4 TREATMENT COMPLIANCE

The qualified individual responsible for dispensing the study treatment will prepare the correct dose according to the randomization schedule. This individual will write the date dispensed and participant number on the study treatment vial label and on the Drug Accountability Record. This individual will also record the study treatment number received by each participant during the study.

6.5 CONCOMITANT THERAPY

Any medication or vaccine (including over-the-counter [OTC] or prescription medicines, approved dietary and herbal supplements, nutritional supplements) used by a participant within 30 days of study screening until the safety follow-up visit must be recorded on the Concomitant Medications eCRF along with reason for use, dates of administration (including start and end dates) and dosage information (including dose and frequency).

The Medical Monitor should be contacted if there are any questions regarding concomitant or prior therapy.

All medication administered to manage AEs should be recorded on the Adverse Event eCRF.

6.5.1 Permitted Therapy

For pre-medication guidelines, refer to Section 6.1.2. Participants who use oral contraceptives with a failure rate of < 1% (See [Appendix 5](#)), hormone-replacement therapy, or other maintenance therapy should continue their use.

The use of limited field palliative radiotherapy during the course of the study should be discussed and agreed by the Investigator on a case-by-case basis with the Medical Monitor in order to exclude overall progressive disease. No delay of study treatment administration is required although participants should not receive study treatment during radiation.

Systemic corticosteroids and TNF- α antagonists may attenuate potential beneficial immunologic effects of treatment with RO7296682 in combination with atezolizumab. Therefore, in situations in which systemic corticosteroids or TNF- α inhibitors would be routinely administered, alternatives (including antihistamines) should be considered. If the alternatives are not feasible, systemic corticosteroids and TNF- α inhibitors may be administered at the discretion of the investigator.

Systemic corticosteroids are recommended, at the discretion of the Investigator, for the treatment of specific AEs when associated with RO7296682/atezolizumab therapy (for details, refer to Section 8.3.9.1, 8.3.9.2, and 8.3.9.3, and Appendix 12).

